**A. SUMMARY:**

Irritable bowel syndrome (IBS) has a worldwide prevalence of 11.2% and is characterized by chronic or recurrent abdominal pain associated with altered bowel habits. Visceral hypersensitivity and dysfunction within the autonomic nervous system (ANS) and immune function are important components contributing to the pathophysiology of irritable bowel syndrome (IBS). Despite recent advances in medical therapies for IBS, a significant subgroup of patients fails to experience satisfactory relief of abdominal pain. Given evidence of anti-inflammatory and anti-nociceptive components of vagal nerve pathways, peripheral field stimulation of the vagus nerve may help reduce visceral sensitivity in IBS patients. Percutaneous electrical nerve field stimulation (PENFS) administered via the IB-Stim device (Innovative Health Solutions, Versailles, IN, USA) has been shown to be efficacious in pediatric patients with abdominal-pain-related functional GI disorders. PENFS was associated with a greater reduction in their worst abdominal pain and overall composite pain scores compared with a sham device after three weeks of treatment. These effects were sustained over an extended follow-up period with minimal to no side effects. This IB-Stim is the first device to be approved by the Food and Drug Administration (FDA) for the treatment of functional abdominal pain in adolescents aged 11-18 with IBS. However, the efficacy of PENFS in adults with IBS is not unknown. We propose to perform a double-blind, randomized, sham-controlled pilot study evaluating the efficacy of PENFS using IB-Stim for the treatment of IBS symptoms in adult patients with IBS.

**B. HYPOTHESIS AND SPECIFIC AIMS:*****Hypotheses:***

In adult patients with IBS, compared to sham therapy, PENFS therapy will be associated with:

1. A greater reduction in IBS Severity Scoring System (IBS-SSS) scores after 4 weeks of treatment and at extended follow-up (8 weeks) compared to baseline in adult patients with IBS
2. An increased proportion of abdominal pain responders after 4 weeks of treatment
3. A greater improvement in weekly average worst abdominal pain score after 4 weeks of treatment and at extended follow-up (8 weeks) compared to baseline.

4. A greater improvement in weekly average bloating scores after 4 weeks of treatment and at extended follow-up (8 weeks) compared to baseline.
5. A greater reduction in cardiosympathetic/vagal tone as measured by heart rate variability (HRV)
6. A greater improvement in disease-specific health related QOL (IBS-QOL).

***Primary Aim:***

1. To compare the efficacy of PENFS therapy versus sham therapy on the improvement of IBS symptom severity in adult IBS patients after 4 weeks of treatment compared to baseline, measured by the mean change in the IBS-SSS.

***Secondary Aims:***

To compare the efficacy of PENFS therapy versus sham therapy on:

1. the change in mean IBS-SSS at week 8 compared to baseline.
2. the proportion of adult patients with IBS who experience at least a 50-point reduction on the IBS-SSS after 4 weeks of treatment and at the extended follow up period at week 8. These patients are considered clinical responders.
3. the proportion of adult patients with IBS who experience an improvement of  $\geq 30\%$  from baseline in weekly average of the daily worst abdominal pain scores after 4 weeks of treatment. These participants are considered a responder.
4. the change in mean weekly average of the daily worst abdominal pain scores after 4 weeks compared to baseline in adult patients with IBS.
5. the change in average weekly abdominal pain symptoms after 4 weeks of treatment and at extended follow-up (8 weeks) compared to baseline, assessed through the PROMIS Gastrointestinal Belly Pain Scale.
6. the change in average daily stool consistency after 4 weeks of treatment compared to baseline, assessed using the Bristol Stool Form Scale (BSFS).
7. the change in average weekly bowel habits after 4 weeks of treatment and at extended follow-up (8 weeks) compared to baseline, assessed through the PROMIS Gastrointestinal Constipation Scale and Gastrointestinal Diarrhea Scale.
8. the change in average weekly bloating symptoms after 4 weeks of treatment and at extended follow-up (8 weeks) compared to baseline, assessed through the PROMIS Gastrointestinal Gas and Bloating Scale.
9. the change in IBS-QOL in adult patients with IBS after 4 weeks of treatment and at extended follow-up (8 weeks) compared to baseline.
10. the change in resting cardio-autonomic tone, i.e. HRV, over 4 weeks of treatment compared to baseline.
11. the safety and tolerability of PENFS therapy versus sham therapy in adult patients with IBS.

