Despite the promise that PENFS has shown in the treatment of adolescents with IBS, there are currently no studies of PENFS in adult IBS patients. The discovery of non-pharmacologic options for adult IBS patients is paramount, because despite recent advances in dietary and medical therapies for IBS, a high percentage of patients do not completely respond to currently available treatments. For instance, in a randomized controlled trial evaluating the efficacy of a diet low in fermentable oligosaccharides, disaccharides, monosaccharides, and polyols (FODMAPs), around 50% of IBS patients did not report clinically significant reductions in IBS severity scores. Linaclotide and plecanatide are both guanylate cyclase agonists that increase intracellular levels of cGMP, activating the cystic fibrosis transmembrane conductance regulator, which leads to secretion of chloride, bicarbonate, and fluid into the intestinal lumen and ultimately accelerates intestinal transit. In animal models, linaclotide also reduces the firing of afferent pain fibers, presumably decreasing visceral hypersensitivity. However, in a phase 3 randomized controlled trial of linaclotide in constipation predominant IBS (IBS-C) patients, 63.4% of patients failed to meet the criteria for endpoint abdominal pain response (improvement of  $\geq 30\%$  from baseline in average daily worst abdominal pain scores). In addition, 48% of patients receiving linaclotide failed to demonstrate clinically meaningful improvement in IBS-related QOL (IBS-QOL). Similarly, in two trials comparing different doses of plecanatide, between 69.8% and 78.5% of IBS-C patients did not achieve the combined endpoint of a  $\geq 30\%$  reduction from baseline in worst abdominal pain plus an increase in  $\geq 1$  complete spontaneous bowel movement.

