The percentage of patients with diarrhea predominant IBS (IBS-D) who reported a clinically significant improvement in abdominal pain was slightly higher in trials of eluxadoline, a peripherally acting mixed  $\mu$ -opioid receptor agonist,  $-\delta$ -opioid receptor antagonist, and  $\kappa$ -opioid receptor agonist. However, after 12 weeks of therapy, between 49.0% and 57.5% of patients still did not meet the endpoint response for improvement in abdominal pain. In addition to low clinical response rates, many of these medications approved for IBS elicit undesirable side effects, which limit their use in certain individuals. Cognitive behavior therapy (CBT) has also been utilized successfully in IBS patients through targeting of the psychological factors that contribute to GI symptoms. However, only a small proportion of IBS patients are actually referred for CBT, largely secondary to barriers including cost, therapist and resource availability, and underlying stigmas.

Overall, the high prevalence of IBS in adults, the negative effect of this disorder on QOL, and the lack of medications that successfully alleviate abdominal pain symptoms illustrate the need to develop effective, non-pharmacologic therapies to better treat IBS patients. Given evidence of anti-inflammatory and anti-nociceptive components of vagal nerve pathways, peripheral field stimulation of the vagus nerve may help reduce the visceral sensitivity component of abdominal pain in IBS patients. This technique of PENFS has already been successfully demonstrated in adolescents with functional abdominal pain, but trials in adults are lacking. If successful, PENFS could represent a favorable, non-pharmacologic treatment option for adult patients with debilitating IBS related abdominal pain and other symptoms.

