**2. *Mandatory inclusion criteria:***

- Adults, aged 18-60 years, who are able to provide written, informed consent
- Patients must meet Rome IV criteria for IBS, confirmed by a gastroenterologist who specializes in functional GI disorders. Any of the IBS bowel habit subtypes (diarrhea, constipation, mixed bowel habits, unclassified) will be allowed.
- Average daily worst abdominal pain score between 4 and 8 (on a 0-10-point rating scale).
- Minimum of 2 days of abdominal pain/week prior to starting trial.
- At least moderate IBS symptom severity with an IBS-SSS  $\geq 175$  (total score range 0-500).

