### ***Assessments and Questionnaires:***

Administration of questionnaires throughout the study is shown in Table 1 and Figure 2.

Patients will provide telephone consent for enrollment into the study. During the this phone call, the investigator will obtain the participant's medical and medication history to check eligibility. After enrollment, patients will complete an online daily questionnaire to assess daily stool consistency (7-point Bristol Stool Form Scale [BSFS]) and a daily question pertaining to daily worst abdominal pain (measured using an 11-point scale) that will be delivered by the smart watch, for one week prior to device placement. If patients do not elect to use the SmartWatch, then they will complete the daily question pertaining to daily worst abdominal pain via an online questionnaire. The questionnaires will provide a baseline for daily worst abdominal pain and stool consistency. In order to be enrolled into the study, patients must have an average daily worst abdominal pain score between 4 and 8, have a minimum of 2 days per week of abdominal pain, and have completed at least 4 out of 7 of the daily worst abdominal pain questionnaires.

If enrollment criteria are met, patients will then present to the UCLA G. Oppenheimer Center for Neurobiology of Stress and Resilience one week after enrollment for their first visit, where they will get a physical examination, complete additional questionnaires, undergo a measurement of HRV, and have the initial PENFS device placed by a trained health care professional (LC, AL, EL). After initial device placement, patients will be instructed to return to UCLA every 7 days (leeway of +/- 2 days in each direction will be allowed) for a total of 4 visits for device replacement and completion of additional questionnaires. Four different devices will be placed in total (at the start of weeks 1, 2, 3, and 4).

Although the IB-Stim device is currently FDA approved for use for 3 consecutive weeks, children in the original study by Kovacic et al actually received 4 consecutive weeks of device treatment. The authors chose to analyze the data after 3 consecutive weeks as children did not return to the clinic after the 4th week of treatment. However, we will analyze IBS symptom severity, abdominal pain, bloating, and bowel habits after the completion of the 4th week of treatment. Again, actual stimulation time is 5 days per week with 2

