#### **Bowel Habit Classification:**

Bowel habits, defined by IBS-C, IBS-D, IBS-mixed type (IBS-M), and IBS-unclassified (IBS-U) will be assessed at baseline using the Rome-IV questionnaire.

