### **Patient Reported Outcomes Measurement Information System (PROMIS)**

The PROMIS Gastrointestinal Belly Pain Scale is a validated questionnaire that assesses the severity of abdominal pain in adult patients over the previous 7 days. This scale incorporates aspects of abdominal pain intensity, discomfort, location, frequency, predictability, and extent to which the pain is bothersome.

The PROMIS Gastrointestinal Gas and Bloating Scale assesses the frequency and intensity/severity of bloating, the appearance of abdominal swelling, flatulence, and abdominal gurgling/rumbling, and the degree to which bloating is bothersome or interferes with daily activities over the past 7 days.

The PROMIS Gastrointestinal Constipation Scale will be used to assess the frequency and intensity of incomplete evacuation, rectal pain, straining, and hard stools. This scale will measure the extent to which constipation is bothersome or interferes with daily activities over the past 7 days. The PROMIS Gastrointestinal Diarrhea Scale will be utilized to evaluate the frequency and severity of loose to watery stools and urgency during the previous 7 days.

Each of the above PROMIS GI scales will be scored using percentile scores that are based on the general population. In order to accurately obtain percentile scores, the scale of each PROMIS question will be converted from 1-5 to 0-4. PROMIS questionnaires assessing bowel habits and the severity of abdominal pain and bloating will be assessed at baseline (visit 1), after each week of treatment (after weeks 1-4), and at extended follow-up. The questionnaires will be completed in person at baseline (visit 1) and after weeks 1-3 (visits 2-4), and via online surveys after 4 weeks and 8 weeks. Response will be assessed by the change in composite abdominal pain scores, bloating scores, constipation scores, and diarrhea scores from baseline to 4 weeks after treatment and from baseline to 8 weeks (extended follow up) after treatment.

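### Secondary aim 6 pools the signed change in Bristol stool score over all IBS subtypes, so benefit in IBS-C and IBS-D offsets and the sign of a difference cannot be read as benefit

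*Combined protocol and SAP*

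**What the plan says.** The secondary aims open with "To compare the efficacy of PENFS therapy versus sham therapy on", and item 6 is "the change in average daily stool consistency after 4 weeks of treatment compared to baseline", measured on the 7-point Bristol Stool Form Scale (BSFS).

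- **Measurement and contrast.** Under Daily Bowel Habits (Section 7), stool form is recorded daily for one week before the first device and one week after the fourth. The change is then compared between PENFS and sham.
- **Test.** Statistical Analysis (Section 9) gives every secondary aim a simple two-sample test of change, with no covariates.
- **Population.** The mandatory inclusion criteria state: "Any of the IBS bowel habit subtypes (diarrhea, constipation, mixed bowel habits, unclassified) will be allowed".
- **Subtype.** Under Bowel Habit Classification, subtype "will be assessed at baseline using the Rome-IV questionnaire". It enters no stated analysis, and no stratification by it is described under Randomization and Masking.
- **Direction of benefit.** None is given for stool form. None of the six hypotheses in Section B concerns it.

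**The concern.** A signed change measures benefit only if benefit has the same direction in everyone. Here it does not. The PROMIS section says the Constipation Scale "will be used to assess the frequency and intensity of incomplete evacuation, rectal pain, straining, and hard stools", and it ties the Diarrhea Scale to loose and watery stools. These are opposite ends of stool form, so improvement has opposite signs in IBS-C and IBS-D whichever way the scale is numbered.

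The plan gives reason to expect both groups. The Background discusses "linaclotide in constipation predominant IBS (IBS-C) patients" and eluxadoline in IBS-D, and Section 1 allows both drugs as concomitant therapy.

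Two things are at stake:

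1. If the device moves stool toward normal in both subtypes, the changes offset and the test can miss a real effect.
2. If the test is significant, the result may be relief in one subtype or worsening in the other. The pooled sign does not separate the two, so it cannot be reported as efficacy.

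**Working it through.** **Inputs from the documents.** There are 35 patients per arm (Sample Size Calculation) and one week of daily 1–7 scores at each time point (Daily Bowel Habits). The test is a two-tailed t-test or Mann–Whitney test (Statistical Analysis). Alpha is not stated; 0.05 is assumed. The plan has no power figure for aim 6 to reproduce, because its sample-size statement concerns abdominal pain. Subtype mix, effect and SD are also not given, so everything after step 1 is illustration.

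**1. Algebra (no SD needed).** Let p_C and p_D be the shares of IBS-C and IBS-D, and b_C and b_D the mean shift toward normal, with other patients unchanged. Up to the direction of scoring,

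Δ = p_C·b_C − p_D·b_D.

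With b_C = b_D = b, Δ = b(p_C − p_D), and the share of the effect retained is |p_C − p_D|/(p_C + p_D):

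- C/D 40/40: 0/80 = 0%
- 30/40: 10/70 = 14%
- 25/50: 25/75 = 33%
- 10/70: 60/80 = 75%
- all IBS-D: 100%

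For the same 1-point benefit, Δ is +0.40 at 70/30, 0.00 at 50/50 and −0.40 at 30/70. The sign follows the enrolment mix.

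**2. Closed-form power.** Take within-subtype SD σ in both arms. The active-arm variance is σ² + (p_C + p_D)b² − Δ². With s² the average of the two arm variances, SE = s√(2/35). Example at 60/40, b = 1, σ = 1: Δ = 0.20, active variance 1 + 1 − 0.04 = 1.96, s = √(2.96/2) = 1.217, SE = 0.291, Δ/SE = 0.69, power 11%.

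| b, σ | 50/50 | 60/40 | 70/30 | Scored toward normal |
|---|---|---|---|---|
| 1.0, 1.0 | 5% | 11% | 29% | 99% |
| 1.0, 1.5 | 5% | 8% | 18% | 80% |
| 0.5, 1.0 | 5% | 7% | 13% | 55% |

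**3. Simulation.** Each scenario has 4,000 trials with integer daily scores. Assumed subtype means are 2.0 (C), 5.8 (D) and 4.0 (M and U, which share the remainder equally; M days vary at random by ±2). Between-patient SD is 0.6, day-to-day SD 1.0 and patient-level change SD 0.9. The same unadjusted t-test is used throughout. Main scenarios were repeated with a new seed and agreed within about 2 points.

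| Scenario (C/D %) | Planned pooled signed | Signed by subtype, C + D | Mean daily \|BSFS − 4\|, all |
|---|---|---|---|
| 1 point in both, 40/40 | 5% | 92% | 67% |
| 1 point in both, 30/40 | 7% | 88% | 56% |
| 1 point in both, 25/50 | 13% | 91% | 63% |
| 1 point in both, 10/70 | 52% | 93% | 66% |
| 1 point, all IBS-D | 97% | 97% | 83% |
| 1 point in both, 25/25, half M or U | 5% | 75% | 35% |
| 0.5 point in both, 40/40 | 5% | 38% | 26% |
| 1 point in one, 0.5 in the other, 40/40 | 10% | 71% | 47% |
| 1 point in both, 40/40, change SD 1.3 | 5% | 71% | 38% |
| Only C benefits, 40/40 | 27% | 37% | 23% |
| Only D benefits, 40/40 | 29% | 39% | 22% |
| 1-point shift the same way in both, 40/40 | 74% | 6% | 5% |
| No effect | 5% | 5% | 5% |

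In the first row the mean arm difference is −0.01 points signed and +0.86 signed by subtype. Mann–Whitney gives 5% and 91%.

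**4. Where the gain comes from.** In the same C + D patients, signed against subtype-signed power is 5% against 92% when both benefit, so that gain comes from the sign. When one subtype benefits it is 34% against 37% (C) and 37% against 39% (D). The roughly 10-point edge in the table for those rows therefore comes from leaving out M and U, which are assumed unchanged.

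**The case against.** - **The stem is generic.** It also covers heart rate variability and safety, so aim 6 could be a two-sided description of stool form, for which a signed change is legitimate. This is fair, and it is why the pooled change should stay. But the plan labels the comparison efficacy and nowhere limits it to description.
- **Bowel benefit is measured elsewhere.** The PROMIS Constipation and Diarrhea scales (aim 7) each have a clear direction, and one of the five IBS-SSS items scores dissatisfaction with bowel habits. This stands and lowers the consequence. It does not make aim 6 interpretable.
- **Severe loss needs near balance and benefit in both subtypes.** This is correct. If one subtype dominates, the sign largely follows it; if only one benefits, little or nothing is lost. The plan sets no mix, however, and the reading problem remains in any mixed sample.
- **Signing by subtype has its own blind spot.** It has 6% power against 74% for a one-way shift, drops M and U, and counts overshoot past normal as benefit. With no subtype stratification, the size and balance of the C + D subset are uncontrolled. All of this stands, and it means the pooled result should be kept alongside.
- **The interim look.** Section 9 plans an interim comparison of group data, and the documents do not show whether it has taken place. A definition changed after it needs a statement that the interim results were not used.

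**Conclusion.** The concern holds. The offset is algebra and rests only on two points: all subtypes are enrolled, and constipation and diarrhea lie at opposite ends of stool form. Under equal benefit the planned contrast keeps between 0% (balanced C and D) and 100% (a single subtype) of the effect. The power figures illustrate the size under assumed mix, effect and SD.

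The unreadable sign does not depend on symmetric benefit. If both subtypes become 1 point firmer at 40/40, the planned test is significant in 74% of trials although IBS-D improves and IBS-C worsens.

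The scope is one of 11 secondary aims in a pilot. The primary endpoint, the sample size and the false-positive rate are not affected. It should be corrected, but it does not threaten the trial.

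**What to change.** Before unblinding, define the direction of benefit from the recorded subtype and keep the planned test. Suggested SAP wording:

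> The Aim 6 efficacy measure is the change from baseline to week 4 in mean daily BSFS, signed by baseline Rome IV subtype: a change toward looser stool is positive in IBS-C and a change toward firmer stool is positive in IBS-D. Arms are compared in IBS-C and IBS-D patients by the planned two-sample test. The change in mean BSFS, pooled and by subtype (C, D, M, U), is reported with 95% confidence intervals as a measure of a one-way shift in stool form, not of benefit.

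An optional supporting measure is the change in mean daily distance from a pre-specified target, which brings M and U back in. The scale midpoint of 4 is one example, for the investigators to confirm. With 3.5 or 4.5 as target, power at 40/40 is 63% or 59% instead of 67%. This measure has less power than the signed test when one subtype dominates or only one benefits.

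The cost is SAP wording. The daily diary and the Rome IV subtype are already collected. If the interim comparison has been run, the SAP should record that the definition was set without reference to it.

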**C. RESEARCH STRATEGY:**

***Background and Clinical Significance:***

**1. Irritable bowel syndrome:**

IBS is a chronic, functional gastrointestinal disorder (GI) disorder characterized by recurring episodes of abdominal pain, bloating, and changes in stool form and frequency. It represents one of the most commonly

diagnosed GI disorders, with a prevalence around 11% worldwide. IBS can negatively affect QOL, reduce work productivity, and lead to increased health care costs and expenditures of health care resources. The pathogenesis of this disorder is complex and likely multifactorial, secondary to abnormalities in intestinal motility, visceral sensitivity, intestinal permeability, immune activation, the microbiome, and brain-gut interactions involving the afferent ascending and the efferent descending pathways.

Visceral hypersensitivity contributes to an intensified severity of abdominal pain in a large proportion of IBS patients, with an estimated prevalence ranging from 33-90% in different studies. This phenomenon refers to altered sensation or enhanced perception of physiologic stimuli within the GI tract, which are interpreted as inducing pain or discomfort. It encompasses the notions of both hyperalgesia, which is defined as an intensified response to stimuli which typically induce pain, and allodynia, which denotes heightened nociception in the setting of benign stimuli. Although the pathophysiology of visceral hypersensitivity in IBS is not completely elucidated, proposed mechanisms include low grade mucosal inflammation, disturbed GI motility, and peripheral and central sensitization of the visceral afferent neuronal pathways.

The interactions between the gut and the central nervous system (CNS) are also exceedingly sophisticated and are responsible for modulating physiologic GI tract homeostasis. The brain-gut axis encompasses both an intrinsic enteric nervous system primarily responsible for gut motility and peristalsis, as well as an extrinsic neural network made up of the vagus nerve (cranial nerve X) and spinal primary afferents that deliver sympathetic and parasympathetic innervation. The vagus nerve represents one of the main components of the parasympathetic nervous system, conveying both afferent and efferent sensory information between the digestive tract and the CNS. Recent studies have also identified the vagus nerve as a potential modulator of intestinal immune function, exerting anti-inflammatory capabilities through the hypothalamic pituitary axis (HPA), the splenic sympathetic anti-inflammatory pathway, and the cholinergic anti-inflammatory pathway. The vagus nerve is also believed to elicit anti-nociceptive effects, primarily through its projections to the nucleus tractus solitarius, which acts as a relay station to the rostral ventral medulla, hypothalamus, amygdala, and spinal cord, as well as through induced activation of the descending noradrenergic and serotonergic systems in the spinal cord that inhibit second order nociception neurons. The amygdala is an integral part of the limbic system, involved in fear conditioning, motivation, reward learning and emotional response to pain. Interestingly, brain imaging studies have demonstrated altered functional connectivity between the amygdala and dorsal anterior insula within the default mode network in hypersensitive IBS.

An imbalance in autonomic nervous system (ANS) function in IBS patients may contribute to heightened visceral sensitivity and altered motility in response to stressors. Indicators of ANS dysfunction, include low vagal tone and increased sympathetic drive, in IBS patients compared to controls. Cardio-vagal autonomic tone, expressed as heart rate variability (HRV), has therefore been utilized as a measure of overall as well as GI specific ANS function, with lower HRV associated with poorer autonomic health. We and others have measured HRV in IBS compared to healthy controls. Studies have also shown that HRV correlates with rectal mucosal blood flow and colonic transit and may be attenuated in patients with IBS compared to healthy controls. Different components of HRV can be used to describe function of the ANS, with power in high frequency (HF) signifying cardiovagal or cardiac parasympathetic activity, and the ratio of low-frequency (LF) power to HF power (LF/HF) representing cardio-sympathetic balance.

Modulating central pain pathways through electrical stimulation of deep brain structures, the vagus nerve, and the spinal cord has also recently gained increased interest in the treatment of chronic pain syndromes, including IBS. However, these aforementioned procedures are quite invasive, limiting their utility in many patients. Rather, a more ideal approach to treating chronic pain in IBS patients may be to potentially access central pain and vagal nerve pathways through peripheral, non-invasive techniques. A study in a rat model of post-inflammatory hyperalgesia showed that PENFS attenuated baseline firing of amygdala and lumbosacral spinal cord neurons, resulting in decreased visceral and somatic hypersensitivity. This intriguing observation subsequently led to a pilot study in humans that demonstrated that a short course of PENFS targeting cranial nerves V, VII, IX, and X, could rapidly and effectively decrease the signs and symptoms of opioid withdrawal without the use of pharmacotherapy. More recently, Kovacic et al conducted a double-blind, randomized, sham-controlled trial evaluating PENFS in children with abdominal-pain-related functional GI disorders. Children in the PENFS group, who effectively underwent peripheral vagal nerve stimulation, had a greater reduction in their worst abdominal pain and overall composite pain scores compared with sham after three weeks of treatment. These effects were sustained over an extended follow-up period with minimal to no side effects.

Despite the promise that PENFS has shown in the treatment of adolescents with IBS, there are currently no studies of PENFS in adult IBS patients. The discovery of non-pharmacologic options for adult IBS patients is paramount, because despite recent advances in dietary and medical therapies for IBS, a high percentage of patients do not completely respond to currently available treatments. For instance, in a randomized controlled trial evaluating the efficacy of a diet low in fermentable oligosaccharides, disaccharides, monosaccharides, and polyols (FODMAPs), around 50% of IBS patients did not report clinically significant reductions in IBS severity scores. Linaclotide and plecanatide are both guanylate cyclase agonists that increase intracellular levels of cGMP, activating the cystic fibrosis transmembrane conductance regulator, which leads to secretion of chloride, bicarbonate, and fluid into the intestinal lumen and ultimately accelerates intestinal transit. In animal models, linaclotide also reduces the firing of afferent pain fibers, presumably decreasing visceral hypersensitivity. However, in a phase 3 randomized controlled trial of linaclotide in constipation predominant IBS (IBS-C) patients, 63.4% of patients failed to meet the criteria for endpoint abdominal pain response (improvement of  $\geq 30\%$  from baseline in average daily worst abdominal pain scores). In addition, 48% of patients receiving linaclotide failed to demonstrate clinically meaningful improvement in IBS-related QOL (IBS-QOL). Similarly, in two trials comparing different doses of plecanatide, between 69.8% and 78.5% of IBS-C patients did not achieve the combined endpoint of a  $\geq 30\%$  reduction from baseline in worst abdominal pain plus an increase in  $\geq 1$  complete spontaneous bowel movement.

The percentage of patients with diarrhea predominant IBS (IBS-D) who reported a clinically significant improvement in abdominal pain was slightly higher in trials of eluxadoline, a peripherally acting mixed  $\mu$ -opioid receptor agonist,  $-\delta$ -opioid receptor antagonist, and  $\kappa$ -opioid receptor agonist. However, after 12 weeks of therapy, between 49.0% and 57.5% of patients still did not meet the endpoint response for improvement in abdominal pain. In addition to low clinical response rates, many of these medications approved for IBS elicit undesirable side effects, which limit their use in certain individuals. Cognitive behavior therapy (CBT) has also been utilized successfully in IBS patients through targeting of the psychological factors that contribute to GI symptoms. However, only a small proportion of IBS patients are actually referred for CBT, largely secondary to barriers including cost, therapist and resource availability, and underlying stigmas.

Overall, the high prevalence of IBS in adults, the negative effect of this disorder on QOL, and the lack of medications that successfully alleviate abdominal pain symptoms illustrate the need to develop effective, non-pharmacologic therapies to better treat IBS patients. Given evidence of anti-inflammatory and anti-nociceptive components of vagal nerve pathways, peripheral field stimulation of the vagus nerve may help reduce the visceral sensitivity component of abdominal pain in IBS patients. This technique of PENFS has already been successfully demonstrated in adolescents with functional abdominal pain, but trials in adults are lacking. If successful, PENFS could represent a favorable, non-pharmacologic treatment option for adult patients with debilitating IBS related abdominal pain and other symptoms.

